Table 10: Toxicity Management Guidelines for Non-Hematological Toxicities (Continued)

Adverse Event ^a	Tafasitamab/Placebo	Lenalidomide	Rituximab
Rash Desquamating (blistering) ≥ Grade 3	If related to tafasitamab/ placebo, discontinue tafasitamab/placebo permanently.	If related to lenalidomide, discontinue lenalidomide permanently.	If related to rituximab, discontinue rituximab permanently.
OR Non-desquamating Grade 4	Note: If the causality cannot tafasitamab/placebo and/or lo permanently.		
Tumor flare reaction ^b Grade 1-2	Continue tafasitamab/ placebo as per Protocol if clinically appropriate.	Continue lenalidomide as per Protocol.	Continue rituximab as per Protocol if clinically appropriate.
Tumor flare reaction ^b ≥ Grade 3	Continue tafasitamab/ placebo as per Protocol if clinically appropriate.	 Interrupt lenalidomide. If the AE resolves to ≤ Grade 1, restart lenalidomide and maintain the same dose level (see Appendix B). 	Continue rituximab as per Protocol if clinically appropriate.
Constipation ≥ Grade 3	Continue tafasitamab/ placebo as per Protocol if clinically appropriate.	 Interrupt lenalidomide. If the AE resolves to ≤ Grade 2, restart lenalidomide and maintain the same dose level (see Appendix B). 	Continue rituximab as per Protocol if clinically appropriate.
Other non-hematologic AEs ≥ Grade 3	Continue tafasitamab/ placebo as per Protocol if clinically appropriate.	 Interrupt lenalidomide. If the AE resolves to ≤ Grade 2, restart lenalidomide and maintain the same dose level (see Appendix B). 	Continue rituximab as per Protocol if clinically appropriate.

^a If, based on medical judgment, the treating physician considers a laboratory parameter change or AE not to be a study drug related toxicity, but to represent a natural fluctuation in or progression of the underlying disease, then it is at the physician's discretion and assessment of the individual risk/benefit ratio to determine whether the participant should be dosed. The decision and rationale behind the decision should be documented in the source data.

6.5.6.1. Tumor Lysis Syndrome Prophylaxis

Participants should hydrate well (orally) during the first week of the first cycle, or for a longer period if clinically indicated. Hydration levels should be adjusted according to age and clinical status of the participant.

In addition, participants may receive TLS prophylaxis (allopurinol, rasburicase, or equivalent) as per institutional guidelines.

If clinically indicated, participants should continue with TLS prophylaxis measures by keeping hydrated and taking the TLS prophylaxis as instructed.

b Tumor flare reaction is defined as constellation of signs and symptoms in direct relation to initiation of therapy. The symptoms/signs include tumor pain, inflammation of visible tumor, hypercalcemia, diffuse bone pain, and electrolyte disturbances (tumor flare reaction is the only AE that will be graded using NCI CTCAE v3.0).

6.5.6.2. Hypogammaglobulinemia

Hypogammaglobulinemia induced by B-cell depletion is a potential on-target toxicity of the anti-CD19 mAb tafasitamab.

In this study, immunoglobulin levels (IgG, IgA, and IgM) are measured at screening and subsequently every 2 cycles starting from Cycle 2 until EOT. Study participants experiencing hypogammaglobulinemia should be managed according to local guidelines.

6.6. Concomitant Medications and Procedures

6.6.1. Participant Monitoring During Tafasitamab or Placebo Infusion

Vital signs should be measured as outlined in Table 3 and Section 8.3.3. All supportive measures consistent with optimal participant care will be provided throughout the study according to institutional standards.

Precautions for anaphylaxis should be observed during tafasitamab or placebo administration. Emergency resuscitation equipment and medications must be readily available. Additional supportive measures should also be available and may include but are not limited to epinephrine, antihistamines, corticosteroids, IV fluids, vasopressors, oxygen, bronchodilators, diphenhydramine, and acetaminophen (paracetamol).

Vital signs are to be obtained before tafasitamab/placebo infusion and then at least 3 times during the infusion (oxygen saturation is not required during the infusion) and as clinically indicated. Participants should continue to be monitored for at least 30 minutes after completion of the tafasitamab/placebo infusion. The frequency or the length of the monitoring period may be adapted if clinically indicated.

6.6.2. Lenalidomide Counseling

Lenalidomide may cause fetal harm when administered to a pregnant woman. Male participants of reproductive potential and participants who are WOCBP may be treated with lenalidomide provided adequate precautions are taken to avoid pregnancy as described in Section 5.1.

Participants will be counseled on lenalidomide's potential risk of teratogenicity at the beginning of each treatment cycle. Additional pregnancy testing and counseling must be performed if a female participant misses her menstruation period or if there is any abnormality in menstrual bleeding.

The investigator will ensure that all participants of reproductive/childbearing potential are able to understand the reason for complying with the special conditions of the pregnancy prevention risk management plan and will also ensure written acknowledgement of participants to adhere to this plan (see Section 5.1).

6.6.3. Prior and Concomitant Therapies

Details of prior, concomitant, or procedural medication or therapy will be captured in the eCRF.

Any prior, concomitant, or procedural medications or therapy (including over-the-counter or prescription medicines, vitamins, vaccines, and/or herbal supplements) given to or taken by the participant up to 4 weeks prior to enrollment and up to 90 days after the last dose of study

treatment or until the participant begins a new anticancer therapy will be recorded in the eCRF. The sponsor will encode all therapy and medication according to the WHO Drug Dictionary. Any addition, deletion, or change in the dose of these medications will also be recorded. Concomitant medications administered after 90 days after the last dose of study treatment should be recorded for SAEs as defined in Section 9.4.

Corticosteroids administered/taken within 3 weeks before ICF signature will be recorded in the eCRF. Participants may continue the medications they were receiving at time of screening. Participants may receive concomitant medications that are medically indicated as standard of care for the treatment of symptoms and intercurrent illnesses such as diabetes, hypertension, bronchial asthma, or chronic obstructive pulmonary disease. Participants may also receive therapy to mitigate side effects of the study treatment as clinically indicated, as well as best supportive care as per institutional guidelines. All concomitant medications should be recorded in the eCRF.

6.6.4. Prophylaxis of Hepatitis B Reactivation

Participants in countries where prophylactic antiviral medications for hepatitis B reactivation are the standard of care may be treated prophylactically. Participants with occult HBV infection, defined as negative HBsAg and positive total HBcAb and negative HBV DNA, are eligible and must undergo ongoing DNA testing (irrespective of prophylactic treatment) as described in Table 4.

6.6.5. Anti-Infection Prophylaxis

Anti-infectious prophylaxis including prophylaxis of opportunistic infections can be given as per institutional guidelines.

6.6.6. Premedication for Tafasitamab or Placebo Infusions/Infusion-Related Reaction Prophylaxis

Tafasitamab or placebo infusions are to be administered to participants after premedication with oral acetaminophen (eg, 650-1000 mg), an antihistamine such as diphenhydramine hydrochloride (eg, 50-100 mg), and glucocorticosteroids (eg, 100 mg IV prednisone or prednisolone or equivalent). The premedication should be administered approximately 30 to 60 minutes prior to starting each infusion.

Premedication is mandatory for the first cycle. For participants who do not experience \geq Grade 2 IRRs or \geq Grade 1 CRS to tafasitamab or placebo during the first cycle, premedication will be optional for subsequent antibody infusions at the discretion of the investigator.

6.6.7. Prophylaxis of Venous Thromboembolism

Prophylaxis of VTE is mandatory for all participants due to increased risk of thrombosis in participants treated with lenalidomide without prophylaxis (Revlimid [lenalidomide] SmPC [2020]). Suggested prophylaxis treatment includes either aspirin (70-325 mg PO daily) or low molecular weight heparin. Participants with a history of VTE or thrombophilia may participate if they are willing to be on full anticoagulation during the treatment. The choice of VTE prophylaxis agent is at the investigator's discretion and should be tailored to the participant's

individual risk/benefit profile by taking into account the individual thrombotic risk, bleeding risk, and quality of compliance with the VTE prophylaxis.

6.6.8. Use of Growth Factors

The use of G-CSF or pegylated G-CSF is optional and should be administered as per institutional guidelines.

6.6.9. Use of Specific Medications Concomitantly With Lenalidomide

The following measurements and precautions should be considered for study participants who receive the following medications concomitantly with lenalidomide.

6.6.9.1. **Digoxin**

When digoxin was coadministered with multiple doses of lenalidomide (10 mg/day), the digoxin C_{max} and AUC_{inf} were increased by 14%.

Consider periodic monitoring of digoxin plasma levels as per investigator's clinical judgment and based on standard clinical practice in participants receiving this medication during administration of lenalidomide.

6.6.9.2. Concomitant Therapies That May Increase the Risk of Thrombosis

Erythropoietic agents or other agents that may increase the risk of thrombosis, such as estrogen-containing therapies, should be used with caution after making a benefit/risk assessment in study participants who receive lenalidomide.

6.6.9.3. Warfarin

Coadministration of multiple doses of lenalidomide (10 mg/day) with a single dose of warfarin (25 mg) had no effect on the PK of lenalidomide or R- and S-warfarin. Expected changes in laboratory assessments of prothrombin time and international normalized ratio were observed after warfarin administration, but these changes were not affected by concomitant lenalidomide administration. It is not known whether there is an interaction between dexamethasone and warfarin.

Close monitoring of the coagulation parameters should be conducted as described in Table 4.

6.6.10. Prohibited Medications and Procedures

6.6.10.1. Anticancer Therapies

No radiotherapy (including limited field radiotherapy) is permitted after the screening PET/CT scan for initial disease assessment has been performed.

The use of concurrent antineoplastic therapies other than study drugs including but not limited to chemotherapies, hormonal therapy, immunotherapy, biological response modifiers, mAbs with or without conjugation, radioisotopic therapies, stem-cell transplant, and targeted small molecules are not permitted during the entire treatment period of this study.

Once the decision to end study treatment has been made, new anticancer treatment is permitted at the discretion of the investigator. Ideally, the safety follow-up visit should be performed prior to

initiating new anticancer therapy. Any new anticancer treatments and the associated response outcomes are to be recorded in the appropriate eCRF.

6.6.10.2. Live Vaccines

Because of the immunosuppressive effects of the study treatment, administration of any live vaccine is not recommended during the treatment period and at least 6 months after the EOT. Thereafter, the decision to administer live vaccines is at the investigator's discretion and should follow local guidelines for lenalidomide in addition to rituximab (the hematological status of individual participant, including B-cell depletion, should be considered).

Please note that this does not apply to COVID-19 vaccines which are nonlive vaccines.

6.7. Treatment After the End of the Study

'Subsequent care for study participants after the discontinuation of study treatment or completion of the study may be given per local institution standard of care.

7. DISCONTINUATION OF STUDY TREATMENT AND PARTICIPANT WITHDRAWAL FROM STUDY TREATMENT

7.1. Discontinuation of Study Treatment

See Table 3 and Table 4 for data to be collected at the time of discontinuation of study treatment and follow-up and for any further evaluations that need to be completed.

7.1.1. Reasons for Discontinuation of Study Treatment

7.1.1.1. Unacceptable Toxicity

The occurrence of unacceptable toxicity not caused by the underlying disease will require that the study treatment (ie, tafasitamab/placebo, lenalidomide, and rituximab) be permanently discontinued. Unacceptable toxicity is defined as follows:

- The occurrence of an AE that is related to study treatment that, in the judgment of the investigator or the sponsor's medical monitor, compromises the participant's ability to continue study-specific procedures or is considered to not be in the participant's best interest.
- In case of drug delay for more than 1 month (4 weeks), the investigator will have to contact the sponsor's medical monitor.

The investigator may also discontinue the treatment to a participant if further participation would be injurious to the participant's health or well-being, in the investigator's medical judgment.

7.1.1.2. Disease Progression

Participants who demonstrate radiologic or metabolic progression of disease as per the Lugano criteria will be considered as having met criteria for disease progression. The EOT visit should be performed as soon as possible, and the participant should continue with the safety and

survival follow-up periods of the study. Any new anticancer therapy (and associated response outcomes) should be captured in the eCRFs.

7.1.1.3. Lack of Efficacy

Participants who, in the treating investigator's decision, require new anticancer therapy due to lack of sufficient response in the absence of either radiologic or metabolic progression of disease per the Lugano criteria will be considered as having met criteria for lack of efficacy. The EOT visit should be performed as soon as possible, and the participant should continue on with the safety and survival follow-up periods of the study. Any new anticancer therapy (and associated response outcomes) should be captured in the eCRFs.

7.1.1.4. Consent Withdrawal

Consent withdrawn means that the participant has explicitly indicated that they do not want to be followed any longer; in this case no further data, except data in the public domain, may be solicited from or collected on the participant.

Participants may choose to discontinue study treatment and remain in the study to be followed for safety, disease progression, and survival per the SoA (see Table 3).

7.1.1.5. Investigator Decision

Investigator(s) also have the right to withdraw participants from the study or from study treatment in the event of illness, AEs, noncompliance, or other reasons concerning the health or well-being of the participant.

7.1.1.6. Pregnancy

Female participants who become pregnant during clinical study participation must discontinue study treatment.

7.1.1.7. Study Termination

Participants must be discontinued from study treatment if the study is terminated by the sponsor or by the local health authority, IRB, or IEC.

7.1.2. Discontinuation Procedures

In the event that the decision is made to permanently discontinue the study treatment, the EOT visit should be conducted. Reasonable efforts should be made to have the participant return for a follow-up visit. These visits are described in Table 3 and Table 4. The last date of the last dose of study treatment and the reason for discontinuation of study /treatment will be recorded in the eCRF.

If a participant is discontinued from study treatment:

- The study monitor or sponsor must be notified.
- The reason(s) for discontinuation must be documented in the participant's medical record and the primary reason for discontinuation must be included in the eCRF and in the source documents.

- The EOT visit should be performed and date recorded.
- The participant enters the follow-up period.
- The status of the participant should be updated to EOT in the IRT.
- Participants must be followed for safety until the time of the follow-up visit or until study treatment—related toxicities resolve, return to baseline, or are deemed irreversible, whichever is longest.

If the participant discontinues study treatment and actively withdraws consent for collection of follow-up data (safety follow-up or disease assessment), then no additional data collection should occur; however, participants will have the option of withdrawing consent for study treatment but continuing in the follow-up period of the study for safety/efficacy assessments.

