7.3. Lost to Follow-Up

A participant will be considered lost to follow-up if they repeatedly fail to return for scheduled visits and is unable to be contacted by the study site.

The following actions must be taken if a participant fails to return to the clinic for a required study visit:

- The site must attempt to contact the participant and reschedule the missed visit as soon as possible and counsel the participant on the importance of maintaining the assigned visit schedule and ascertain whether or not the participant wishes to and/or should continue in the study.
- Before a participant is deemed lost to follow-up, the investigator or designee must
 make every effort to regain contact with the participant (where possible, 3 telephone
 calls and, if necessary, a certified letter to the participant's last known mailing address
 or local equivalent methods). These contact attempts should be documented in the
 participant's medical record.
- Should the participant continue to be unreachable, they will be considered to have withdrawn from the study.

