8.9.3. Survival Follow-Up/Completion of Study

All participants will be followed for survival status every 12 weeks (\pm 4 weeks) until death, lost to follow-up, withdrawal of consent for survival follow-up, completion of the 5-year follow-up interval, or the end of the study.

For participants who have entered the survival follow-up period, sites will continue to collect
data regarding initiation of new anticancer treatment
and report OS. For participants who do not intend to return to the
study investigator for their ongoing care, follow-up will be maintained by telephone contact,
patient records, and public records/databases at intervals of no longer than 12 weeks.

Additional survival assessments may be performed outside the 12-week interval if a survival update is required for an interim assessment to meet safety or regulatory needs.

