10.4.1.2.3. Overall Survival in the Follicular Lymphoma Population

Overall survival is defined as the time from randomization until death from any cause. Participants who are not reported as a death at the time of the analysis cutoff will be censored at the date of last known alive, regardless if a new antilymphoma therapy was started.

All participants should be followed until death or until the end of study as specified in the Protocol, whichever comes first. The follow-up data should contain the date the participant was last seen alive/last known alive, the date of death, and the reason of death ("disease progression," "adverse event," or "other").

Overall survival will be compared and analyzed in the same manner as described above in Section 10.4.1.1 for the PFS.

Key secondary analysis of OS will be performed for participants with FL in the FAS. The analysis will be performed at the time of final analysis.

Additional sensitivity analyses will be performed as mentioned in Section 10.4.1.6.

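### Section 7.1.2 stops all data collection once an off-treatment participant withdraws consent for safety follow-up or disease assessment, while Section 8.9.3 continues survival follow-up until consent for survival follow-up itself is withdrawn

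*Protocol*

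**What the plan says.** Three protocol sections state when data collection ends.

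- **Section 7.1.2 (Discontinuation Procedures).** It applies when a participant has stopped study treatment and "actively withdraws consent for collection of follow-up data (safety follow-up or disease assessment), then no additional data collection should occur". Survival is neither named nor exempted. The alternative offered is to withdraw from treatment only and stay in follow-up for safety and efficacy assessments.
- **Section 8.9.3 (Survival Follow-Up/Completion of Study).** "All participants will be followed for survival status every 12 weeks". Besides death, the stops are "lost to follow-up, withdrawal of consent for survival follow-up, completion of the 5-year follow-up interval, or the end of the study". For participants who will not return to the site, "follow-up will be maintained by telephone contact, patient records, and public records/databases at intervals of no longer than 12 weeks".
- **Section 7.1.1.4 (Consent Withdrawal).** When a participant explicitly does not want to be followed at all, "no further data, except data in the public domain, may be solicited from or collected on the participant".

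The OS analysis text in Protocol 10.4.1.2.3 adds: "All participants should be followed until death or until the end of study as specified in the Protocol, whichever comes first". SAP 7.3.2.3 censors participants without a reported death at the last date known alive, or at the cutoff if that is earlier. It does not say which follow-up rule governs. OS in FL is the last step of the hierarchical test, at 2-sided 5% at the final analysis (SAP 3.2). It also has a futility look at the time of the PFS primary analysis (SAP 9.2).

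**The concern.** Section 8.9.3 treats consent to survival follow-up as a separate level of consent. Section 7.1.2 does not recognise that level: withdrawing consent for scans or safety visits ends everything. Read literally, it is also stricter than the full-withdrawal rule in 7.1.1.4, which keeps public-domain data available after a broader refusal.

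Take a participant who withdraws consent for disease assessment but would accept a telephone call every 12 weeks. A site following 7.1.2 stops, and OS is censored at about that date. A site following 8.9.3 continues, and a later death counts. Both sites comply with the protocol. At stake is the completeness of death data for an alpha-controlled endpoint, and deaths that were never collected cannot be recovered at the analysis.

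**Working it through.** **Text.** The same participant under each rule (off treatment, consent withdrawn for scans or safety visits, no refusal of survival contact):

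- 7.1.2: collection stops; OS censored at last known alive.
- 8.9.3: none of the listed stops has occurred; contact continues; a later death is an OS event.
- 7.1.1.4: not triggered, because the participant has not refused all follow-up. Even if it were, a death on public record could be used.

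The parenthesis in 7.1.2 could be read as needing withdrawal from both kinds of assessment. The conflict remains on that reading, because survival contact has still not been refused.

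**Inputs (Protocol 10.1; SAP 3.3 and 9.2.1).** 528 FL participants, 264 per arm; control median OS 120 months; HR 0.65; uniform accrual over 21 months; PFS primary analysis at month 33.5; final analysis at about month 96. Exponential hazards are λc = ln 2/120 = 0.005776 and λe = 0.65 × λc = 0.003755 per month.

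**The SAP's own figure.** With complete follow-up, the probability of death by month T is 1 − [exp(−λ(T−21)) − exp(−λT)]/(21λ). At T = 33.5, 448 participants without dropout give 46.2 deaths. Using 528 with exponential dropout of 15% per 12 months gives 46.6. Either fits the SAP's approximately 47. With 528 and no dropout the figure is 54.5.

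**Final analysis, complete follow-up.** At T = 96 the probabilities are 0.3894 (control) and 0.2744 (experimental). Deaths = 264 × (0.3894 + 0.2744) = 175.2. Schoenfeld power is Φ(0.5 × |ln 0.65| × √d − 1.96) = Φ(2.851 − 1.960) = 81.4%.

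**Deaths missed under 7.1.2 (illustration).** Assume a share w withdraws this way, uniformly over the first 24 months after randomization, with no other dropout. Per arm, the chance that death falls between withdrawal and month 96 is (1 − exp(−24λ))/(24λ) minus the probability of being alive at the cutoff:

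- control: 0.9338 − 0.6106 = 0.3231
- experimental: 0.9563 − 0.7256 = 0.2307

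Deaths missed = 264 × w × 0.5538 = 146.2 × w.

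**With the follow-up limit.** Protocol 4.2 gives about 6 years per participant. The last participant enters at month 21, so by month 96 everyone has at least 75 months since randomization and a 72-month limit binds for all. Deaths = 264 × [(1 − exp(−72λc)) + (1 − exp(−72λe))] = 264 × (0.3403 + 0.2369) = 152.4, power 75.8%. Deaths missed = 264 × w × [(0.9338 − 0.6597) + (0.9563 − 0.7631)] = 123.3 × w.

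| w | Participants | Missed, no limit | Power (from 81.4%) | Missed, 72-month limit | Power (from 75.8%) |
|---|---|---|---|---|---|
| 2% | 10.6 | 2.9 | 80.7% | 2.5 | 75.1% |
| 5% | 26.4 | 7.3 | 79.7% | 6.2 | 74.0% |
| 10% | 52.8 | 14.6 | 77.9% | 12.3 | 72.2% |
| 15% | 79.2 | 21.9 | 76.0% | 18.5 | 70.3% |

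At the OS futility look (month 33.5), the same assumptions give 0.5, 1.3, 2.7 and 4.0 deaths missed out of 54.5.

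**The case against.** The strongest reply is that 8.9.3 is the specific rule for survival, covers everyone and has its own stop, so a sensible site would apply it. Section 7.1.1.4 also says that a participant may stop treatment and still be followed for safety, progression and survival. After progression, participants move to survival follow-up and protocol scans end, so fewer people remain who could withdraw from disease assessment alone. The consent form may set out the tiers, and the consent pages are not in the public copy. All of this limits the size. None of it removes the conflict, because 7.1.2 states a blanket stop and does not refer to 8.9.3.

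Three stronger readings are tempting, and the documents do not support them.

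- *Declining a scan ends OS follow-up.* The trigger in 7.1.2 is active withdrawal of consent after stopping treatment. A missed or declined scan does not meet it.
- *Unreachable participants also fall under 7.1.2.* Section 7.3 says "Should the participant continue to be unreachable, they will be considered to have withdrawn from the study". Someone who cannot be reached has not actively withdrawn consent, and 8.9.3 already lists loss to follow-up as a separate stop.
- *The power loss is large, because 15% per year reproduces the SAP's 47 deaths.* The match proves little, since 448 participants with no dropout give 46.2. The sample-size section uses 15% as a single proportion (448/0.85 = 527.1, rounded up to 528). Dropout also includes people whom both rules would stop following.

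**Conclusion.** The conflict stands on the current text. Section 7.1.2, followed as written, gives up survival data that 8.9.3 would collect, for a formally tested endpoint. Deaths on public record might still be captured under 7.1.1.4, so the loss is not absolute across the protocol.

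The number of participants affected is not in the documents. The 2% to 15% range is an assumption, as are the uniform timing over 24 months, exponential survival at the SAP's medians and the absence of other dropout. At 2% to 5% the cost is under 2 power points; at 15% it is about 5 to 6 points, depending on whether the follow-up limit is applied. The absolute power figures depend on that limit; the conflict does not.

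A reader might infer that those who withdraw have a worse prognosis and that the censoring therefore biases the hazard ratio. The documents say nothing about who withdraws, so bias is possible but its presence, direction and size cannot be stated. This point concerns OS and makes no claim about the primary PFS comparison.

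**What to change.** In Section 7.1.2, replace the blanket stop with a stop limited to what was refused:

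- the assessments for which consent was withdrawn end;
- survival status continues under 8.9.3 unless consent for survival follow-up is also withdrawn;
- public-domain data may be used as in 7.1.1.4 where local law allows.

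One sentence in SAP 7.3.2.3 could then confirm whether deaths found in public records after withdrawal count as OS events.

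The cost is a wording change and a reminder to sites. No visits or procedures are added, because the 12-weekly survival contact already exists. The downside is that consent-form wording must be checked, so that continued survival contact matches what participants agreed to. The benefit depends on making the change while survival follow-up is still open.
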